10.2.3 Treatment Period

The treatment period is defined as the time of first dose on Day 1 through Day 7. Treatment should be initiated as soon as possible after snakebite envenoming.

The following procedures will be performed on Day 1 of the Treatment Period:

10.2.3.1 Day 1 (Dosing, 0 Hours)

- Administer IP (oral loading dose) (Day 1, 0 Hours) in treatment and placebo arms
- Record time to SOC and IP intervention
- Record details (type, brand, number of vials) of antivenom use from the point of the index snakebite through the completion of all antivenom use for this patient
- Record hospitalization details
- Record pulmonary support interventions
- Record any concomitant therapy
- Assess and record any AEs

10.2.3.2 Day 1 (1 Hour)

• Perform CGI-I (assess compared to Baseline CGI-I)

10.2.3.3 Day 1 (2 Hours)

• Perform CGI-I (assess compared to Baseline CGI-I)

10.2.3.4 Day 1 (3 to 4 Hours)

- Perform CGI-I (assess compared to Baseline GGI-I)
- Measure vital signs per institutional practice
- Perform individual assessments pertaining the SSS, prior to administration of repeat doses of antivenom, if required (clinical evaluation of the actual SSS point score will be performed after completion of the study):
 - Local wound severity

OPX-PR-01

- Pulmonary severity
- Cardiovascular severity
- Gastrointestinal severity
- Hematologic severity
- Renal severity
- Nervous system severity
- Measure Head-Lift duration (0 to 5 seconds)
- Perform NPRS
- Measure grip strength
- Collect blood and urine for the following laboratory assessments:
 - CBC
 - Serum chemistry
 - Hemolysis (Free hemoglobin, haptoglobin, LDH)
 - PT, PTT, thrombin time, INR
 - Absolute fibrinogen
 - CK
 - sPLA₂ levels at 3 hours post-dose as described in Section 10.2.1
- Record concomitant medications and therapies (e.g., prescription and nonprescription medications, pain medications)
- Perform PGIC
- In sedated, endotracheally intubated subjects, perform additional assessments according to instructions in Section 10.3.1.7.
- Collect PK samples from subset of subjects as described in Section 10.3.2.1
- Record SOC treatment
- Record hospitalization details
- Record pulmonary support interventions
- Assess and Record AEs

10.2.3.5 Day 1 (5 to 6 Hours)

Measure vital signs per institutional practice

OPX-PR-01

 Perform individual assessments pertaining the SSS, prior to administration of repeat doses of antivenom, if required (clinical evaluation of the actual SSS point score will be performed after completion of the study):

- Local wound severity
- Pulmonary severity
- Cardiovascular severity
- Gastrointestinal severity
- Hematologic severity
- Renal severity
- Nervous system severity
- Measure Head-Lift duration (0 to 5 seconds)
- Perform NPRS
- Measure grip strength
- Collect blood and urine for the following laboratory assessments:
 - CBC
 - Serum chemistry
 - LFTs
 - Hemolysis (Free hemoglobin, haptoglobin, LDH)
 - PT, PTT, thrombin time, INR
 - Absolute fibrinogen
 - CK
 - sPLA₂ levels at 6 hours post-dose as described in Section 10.2.1
- Record concomitant medications and therapies (e.g., prescription and nonprescription medications, pain medications)
- Perform CGI-I
- Perform PGIC
- In sedated, endotracheally intubated subjects, perform additional assessments according to instructions in Section 10.3.1.7.
- Collect PK samples from subset of subjects as described in Section 10.3.2.1
- Continue SOC treatment
- Record hospitalization details

OPX-PR-01

- Record pulmonary support interventions
- Assess and record AEs

10.2.3.6 Day 1 (8 to 10 Hours)

- Measure vital signs per institutional practice
- Perform individual assessments pertaining the SSS, prior to administration of repeat doses of antivenom, if required (clinical evaluation of the actual SSS point score will be performed after completion of the study):
 - Local wound severity
 - Pulmonary severity
 - Cardiovascular severity
 - Gastrointestinal severity
 - Hematologic severity
 - Renal severity
 - Nervous system severity
- Measure Head-Lift duration (0 to 5 seconds)
- Perform NPRS
- 12-lead ECG
- Measure grip strength
- Collect blood and urine for the following laboratory assessments:
 - CBC
 - Serum chemistry
 - Hemolysis (Free hemoglobin, haptoglobin, LDH)
 - PT, PTT, thrombin time, INR
 - Absolute fibrinogen
 - CK
 - sPLA₂ levels as described in Section 10.2.1
 - Biomarkers (CRP, and D-dimer)
- Perform CGI-I
- Perform PGIC

OPX-PR-01

• In sedated, endotracheally intubated subjects, perform additional assessments according to instructions in Section 10.3.1.7.

- Perform PSFS
- Collect PK samples from subset of subjects as described in Section 10.3.2.1
- Record concomitant medications and therapies (e.g., prescription and nonprescription medications, pain medications)
- Continue SOC treatment
- Record hospitalization details
- Record pulmonary support interventions
- Assess and record AEs

10.2.3.7 Day 2

- Continue BID oral treatment with the IP
- Perform physical examination
- Measure vital signs per institutional practice
- Perform individual assessments pertaining the SSS (clinical evaluation of the actual SSS point score will be performed after completion of the study):
 - Local wound severity
 - Pulmonary severity
 - Cardiovascular severity
 - Gastrointestinal severity
 - Hematologic severity
 - Renal severity
 - Nervous system severity
- Measure Head-Lift duration (0 to 5 seconds)
- Perform NPRS
- Measure grip strength
- Collect blood and urine for the following laboratory assessments:
 - CBC
 - Serum chemistry

OPX-PR-01

- LFTs
- Hemolysis (Free hemoglobin, haptoglobin, LDH)
- PT, PTT, thrombin time, INR
- Absolute fibrinogen
- CK
- Urinalysis
- sPLA₂ levels as described in Section 10.2.1
- Biomarkers (CRP, and D-dimer)
- Perform CGI-I
- Perform PGIC
- Perform PSFS
- Assess C-SSRS (Frequent Screening Form)
- In sedated, endotracheally intubated subjects, perform additional assessments according to instructions in Section 10.3.1.7
- Record concomitant medications and therapies (e.g., prescription and nonprescription medications, pain medications)
- Continue SOC treatment
- Record hospitalization details
- Record pulmonary support interventions
- Assess and Record AEs

10.2.3.8 Day 3

- Continue BID oral treatment with the IP
- Perform physical examination
- Measure vital signs per institutional practice
- Perform individual assessments pertaining the SSS (clinical evaluation of the actual SSS point score will be performed after completion of the study):
 - Local wound severity
 - Pulmonary severity
 - Cardiovascular severity

OPX-PR-01

- Gastrointestinal severity
- Hematologic severity
- Renal severity
- Nervous system severity
- Measure Head-Lift duration (0 to 5 seconds)
- Perform NPRS
- Measure grip strength
- Collect blood and urine for the following laboratory assessments:
 - CBC
 - Serum chemistry
 - LFTs
 - CK
 - Hemolysis (Free hemoglobin, haptoglobin, LDH)
 - PT, PTT, thrombin time, INR
 - Absolute fibrinogen
 - Urinalysis
 - sPLA₂ levels as described in Section 10.2.1
 - Biomarkers (CRP, and D-dimer)
- Collect PK samples from subset of subjects as described in Section 10.3.2.1
- Perform CGI-I
- Perform PGIC
- Perform PSFS
- Assess C-SSRS (Frequent Screening Form)
- In sedated, endotracheally intubated subjects, perform additional assessments according to instructions in Section 10.3.1.7
- Record concomitant medication and therapies (e.g., prescription and nonprescription medications, pain medications)
- Continue SOC treatment
- Record hospitalization details
- Record pulmonary support interventions

Assess and Record AEs

10.2.3.9 Day 7 (7 Days \pm 1 Day)

- Continue BID oral treatment with the IP
- Perform physical examination
- Measure vital signs per institutional practice
- Perform individual assessments pertaining the SSS (clinical evaluation of the actual SSS point score will be performed after completion of the study):
 - Local wound severity
 - Pulmonary severity
 - Cardiovascular severity
 - Gastrointestinal severity
 - Hematologic severity
 - Renal severity
 - Nervous system severity
- Measure Head-Lift duration (0 to 5 seconds)
- Perform NPRS
- 12-lead ECG
- Measure grip strength
- Collect blood and urine for the following laboratory assessments:
 - CBC
 - Serum chemistry
 - LFTs
 - PT, PTT, thrombin time, INR
 - Absolute fibrinogen
 - Urinalysis
 - sPLA₂ levels as described in Section 10.2.1
 - Biomarkers (CRP, and D-dimer)
- Collect PK samples from all subjects as described in Section 10.3.2.1
- Perform CGI-I

OPX-PR-01

- Perform PGIC
- Perform PSFS
- Assess C-SSRS (Since Last Visit Form)
- In sedated, endotracheally intubated subjects, perform additional assessments according to instructions in Section 10.3.1.7
- Record concomitant medications and therapies (e.g., prescription and nonprescription medications, pain medications)
- Continue SOC treatment
- Record hospitalization details
- Record pulmonary support interventions
- Assess and Record AEs

10.2.3.10 Day 14 (14 Days \pm 2 Days)

- Perform physical examination
- Measure vital signs per institutional practice
- Perform individual assessments pertaining the SSS (clinical evaluation of the actual SSS point score will be performed after completion of the study):
 - Local wound severity
 - Pulmonary severity
 - Cardiovascular severity
 - Gastrointestinal severity
 - Hematologic severity
 - Renal severity
 - Nervous system severity
- Measure Head-Lift duration (0 to 5 seconds)
- Perform NPRS
- Measure grip strength
- Collect blood and urine for the following laboratory assessments:
 - CBC
 - Serum chemistry

OPX-PR-01

- PT, PTT, thrombin time, INR
- Absolute fibrinogen
- Biomarkers (CRP, and D-dimer)
- Perform CGI-I
- Perform PGIC
- Perform PSFS
- Assess C-SSRS (Since Last Visit Form)
- Record medical history, including current medications and therapies (e.g., prescription and nonprescription medications, pain medications)
- Continue SOC treatment
- Record hospitalization details
- Record pulmonary support interventions
- Assess and Record AEs

10.2.3.11 Day 28 (End of Study Visit)

- Perform physical examination
- Measure vital signs per institutional practice
- Measure body weight
- Perform individual assessments pertaining the SSS (clinical evaluation of the actual SSS point score will be performed after completion of the study):
 - Local wound severity
 - Pulmonary severity
 - Cardiovascular severity
 - Gastrointestinal severity
 - Hematologic severity
 - Renal severity
 - Nervous system severity
- Measure Head-Lift duration (0 to 5 seconds)
- Perform NPRS
- 12-lead ECG

OPX-PR-01

- Measure grip strength
- Collect blood and urine for the following laboratory assessments:
 - CBC
 - PT, PTT, thrombin time, INR
 - Absolute fibrinogen
 - Serum chemistry
 - LFTs
 - Urinalysis
 - Serum pregnancy test (subjects of childbearing potential only)
- Perform CGI-I
- Perform PGIC
- Perform PSFS
- Assess C-SSRS (Since Last Visit Form)
- Record concomitant medications and therapies (e.g., prescription and nonprescription medications, pain medications)
- Continue SOC treatment
- Record hospitalization details
- Record pulmonary support interventions
- Assess and Record AEs

10.3 Assessments

10.3.1 Efficacy Assessments

Assessments used in this protocol include additional bedside assessments for endotracheally intubated subjects, the SSS, the CGI-I, the PGIC, the PSFS, the NPRS, grip strength, Head-Lift duration, and analgesic use. Each study subject will be evaluated using the PGIC, PSFS, grip strength, or NPRS at the timepoints indicated in the Schedule of Events (Table 1). The SSS evaluation is provided as a checklist in Appendix A and B; all other forms and assessments are provided in Appendix C.

Acute changes in a patient's clinical status that occur during the first 24 hours, including the period between enrollment and administration of IP, but outside of a "Scheduled Assessment" timepoint should be recorded as "Unscheduled Visit" in ePRO or EDC systems, as appropriate.

Individuals that cannot respond to assessments due to severity of snakebite envenoming will be given a score corresponding to the worst score available in the assessment. Specific assessments and unable to respond scores are:

- PSFS = 0 (Unable to perform activity)
- PGIC =10 (Feel much worse)
- Grip Strength = 0

Missing measurements of the SSS at 6 or at 9 hours won't be replaced for the purpose of calculating the primary outcome. If the SSS at one of these timepoints is missing, the average SSS will be based solely on the SSS recorded for the other time point.

10.3.1.1 Composite Snakebite Severity Scale

The SSS (Dart RC et al., 1996) is a tool that was developed to measure the severity of envenoming based on 6 body system categories. The composite SSS score to be used, herein, is based on 7 categories and includes respiratory paralysis, acute renal failure, major thrombotic events, and death.

The renal system category will be used to characterize the severity of acute renal injury (scoring provided in appendix B). The baseline value for serum creatinine will be defined as the most recent serum creatinine in the past year, if one is available, or as the normal expected value for the patient.

Severe weakness or paralysis, including respiratory paralysis, will be scored a 3 in the nervous system section. Major thrombotic events will be scored in the appropriate SSS category as clinically presented. Death will be scored as the maximum score in each section.

The seven body systems are included as follows:

- Local wound (e.g., pain, swelling and ecchymosis)
- Pulmonary
- Cardiovascular
- Gastrointestinal
- Hematologic
- Nervous system
- Renal

OPX-PR-01

Each of these 7 categories are graded at levels from Grade 0 to Grade 3 (pulmonary, cardiovascular, gastrointestinal, nervous, and renal systems) or Grade 0 to Grade 4 (local wound and hematologic symptoms). A higher score indicates worse signs or symptoms. SSS scores will be performed by study personnel using the scoring sheet provided in Appendix B. At each assessment timepoint, each of the 7 SSS subscores should be recorded and a justification for each score should be provided.

10.3.1.2 Clinical Global Impression-Improvement

The CGI-I provides a clinician-based overall rating of the patient's condition (i.e., severity, distress, impairment and impact on functioning) in comparison to previous clinical status. The CGI-I should be determined using all available information, such as interviews with patients and family members, reports from other providers (including prehospital and transfer reports), medical records, and prior laboratory data (Busner and Targum, 2007) (Appendix C1). Baseline rating should be in comparison to previous patient status. Additional CGI-I should be performed on Day 1 at 1, 2, and 3 hours post initial dose, then follow normal assessment schedule as provided in the Schedule of Events. All post-baseline CGI-I assessments should be compared to baseline CGI-I.

The CGI-I is defined as a selection of one of the following at each assessment period:

- 1 = very much improved since the initiation of treatment
- 2 =much improved
- 3 = minimally improved
- 4 = no change from baseline (the initiation of treatment)
- 5 = minimally worse
- 6 = much worse
- 7 = very much worse since the initiation of treatment

10.3.1.3 Patient Global Impression of Change Scale

The PGIC (Appendix C2) is a short, widely used, qualitative metric to evaluate a subject's belief regarding the efficacy of treatment. This metric consists of a question asking the subject to score their overall change in symptoms, followed by a question regarding the degree of change.

10.3.1.4 Patient-Specific Functional Scale

The PSFS (Appendix C3) is a questionnaire that can be used to quantify activity limitation and measure functional outcome for patients. The clinician asks each subject to identify up to 3 activities that they are unable to perform due to their medical condition, and asks the subject to rate their ability to perform that activity on a scale from 0 (unable to perform) to 10 (able to perform to the same ability as before the medical condition).

10.3.1.5 Numeric Pain Rating Scale

The NPRS is a numerical metric that is used by patients to evaluate pain they are experiencing. The NPRS may be adapted or replaced as necessary for pediatric subjects (Appendix C4).

10.3.1.6 Columbia-Suicide Severity Rating Scale

The C-SSRS is a short questionnaire, available in 114 languages, that is designed to provide suicide risk assessment. Ultimately, the determination of the presence of suicidal ideation or behavior depends on the judgment of the individual administering the scale and patients indicating ideation of self-harm at any point in the study should be evaluated and treated per institutional practice.

Generally, the C-SSRS should be administered at Baseline, or at the earliest time point clinically allowable (ideally on Day 1) and then at every study visit through Day 28. For the sake of this clinical study, modified versions of the C-SSRS will be administered at different study visits to minimize burden on study subjects. The modified C-SSRS forms are provided in Appendix C5 as the "C-SSRS Baseline/Screening Form" and the "C-SSRS Since Last Visit Form." These modified C-SSRS forms should be administered to subjects as follows:

- The C-SSRS Baseline/Screening Form should be administered at Baseline (on Day 1) or as early as clinically allowable, performance should not delay care,
- The C-SSRS Since Last Visit Form should be administered for the remaining visits on Days 2, 3, 7, 14, and 28.

10.3.1.7 Additional Assessments on Endotracheally Intubated Subjects

For SSS nervous system examination in endotracheally intubated patients:

- 1. Record current mechanical ventilation modes and all relevant ventilator settings; e.g. control mode ventilation, weaning mode ventilation, or independent breathing without any support. Commonly used ventilatory modes are listed in Appendix C7.
- 2. Remove sedation (and if applicable, paralytics) sufficiently early for awake examination (e.g. until patient is sufficiently awake to follow commands) per institutional practice
- 3. In subjects able to respond and follow commands
 - a. Once subject is sufficiently alert, record time from removal of sedation to examination and describe the level of alertness/sedation per institutional practice. If a sedation score is typically used, it should be recorded and the scoring system used should be specified.
 - b. Measure Head-Lift duration in the same manner as for non-intubated subjects. With the patient supine on a flat bed, ask the subject to raise head approximately

8 cm off the bed. Record the duration of time that the subject can lift and hold head approximately 8 cm off the bed, up to a maximum of 5 seconds.

- c. Perform and record the SSS.
- 4. In subjects who are unable to achieve an acceptable level of alertness 60 minutes after discontinuation of sedation (and if applicable, paralytics), record SSS and Head-Lift duration.
- 5. In subjects who meet institutional weaning criteria, record mode and settings of mechanical ventilation as listed in Appendix C7 to indicate the level of support/independence to which they have progressed.
- 6. In subjects who meet institutional criteria for immediate extubation but deferred or postponed as per institutional practice (e.g., meets criteria for extubation at night but not extubated until the next day), note patient status and record mode and settings of mechanical ventilation (see Appendix C7).
- 7. If used per institutional practice, record negative inspiratory force (NIF)/maximum inspiratory pressure (MIP).

10.3.1.8 Grip Strength

Grip strength will be evaluated using a dynamometer, as a measure of the severity of the neurological effects of snakebite. Grip strength should be measured in affected hand if the bite occurred in upper extremity or the dominant hand if bite occurred elsewhere.

10.3.1.9 Head-Lift duration

Patient should be supine on flat bed. Ask patient to lift their head approximately 8 cm off of bed. Measure the duration in seconds that the patient can hold their head approximately 8 cm off of the bed. Stop after 5 seconds (i.e. maximum duration is 5 seconds).

10.3.1.10 Analgesic Use

For each assessment time point, the patient's current analgesic use will be characterized by the clinical research team based on the strongest category of analgesic taken to treat snakebite-related pain.

10.3.2 Pharmacokinetics

10.3.2.1 Pharmacokinetic Analysis Methods

The concentration of varespladib-methyl in plasma will be evaluated in a subset of both adult and pediatric subjects on Days 1 and 3 and in all subjects on Day 7. PK sampling will only be performed for a total of 20 adult and pediatric subjects on Days 1 and 3, and all subjects on Day 7. Once 20 subjects have provided PK samples for Days 1 and 3, sites will be notified by the

OPX-PR-01

sponsor to discontinue Day 1 and 3 PK sampling. Efforts will be made to include at least 4 pediatric subjects from each age tier (5 to < 11, 11 to < 18 years old) in the PK analysis. PK samples will be collected on Days 1 and 3 as follows:

- Day 1 (20 adult and pediatric subjects): pre-dose and 0.5, 1, 2, 4, 6, 8, and 12 (pre-second dose) hours post-dose.
- Day 3 (20 adult and pediatric subjects): pre-dose and 0.5, 1, 2, 4, and 6 hours post-dose.
- Day 7 (all 110 subjects): pre-dose.

The PK characterization of drug concentrations for each dose to be profiled will use noncompartmental analysis (NCA). Additional details of the parameters and their calculation and evaluation is included in the Statistical Analysis Plan (SAP).

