- s PLA₂ sampling will be performed for all subjects on Day 1 (pre-dose and 1, 3, 6, and 9 hours post-first dose), and on Day 2, Day 3, and Day 7 (pre-dose). sPLA₂ in serum and PK samples will be processed and analyzed in a central laboratory, not at individual sites.
- PK sampling will only be performed for a total of 20 adult and pediatric subjects on Days 1 and 3, and all subjects on Day 7. Once 20 subjects have provided PK samples for Days 1 and 3, sites will be notified by the sponsor to discontinue Day 1 and 3 PK sampling. Subjects will be enrolled for PK analysis as follows: Day 1 20 subjects, pre-dose and 0.5, 1, 2, 4, 6, 8, and 12 (pre-second dose) hours; Day 3 20 subjects, pre-dose and 0.5, 1, 2, 4, 6 hours; Day 7 all subjects, pre-dose.

Figure 1 Study Schematic

- a. Because snakebite subjects are considered critically ill and will arrive in an emergency department setting, Screening, Baseline evaluation, randomization, and treatment must all take place on Study Day 1
- b. Assessments (see Schedule of Events) must be performed at the following times post-initial dose: 3 to 4 hours, 5 to 6 hours, 8 to 10 hours, 2 days (12 to 18 hours after last Day 1 measurements), 3 days (approximately 24 hours after Day 2 measurements), 7 days ± 1 day, 14 days ± 2 days, and 28 days ± 3 days
- c. The varespladib-methyl dosing for adult subjects is a 500 mg loading dose, a 250 mg dose approximately 12 hours later, then 250 mg BID for the remainder of the study period; pediatric subjects (ages 5 to < 18) will be administered doses of varespladib-methyl determined by allometric scaling, provided as 50 mg capsules, depending on age (see Section 7.3). Abbreviations: BID = twice daily; SOC = standard of care; yr = years

3		TABLE OF CONTENTS	
1	APF	PROVAL SIGNATURES	2
2	PRO	OTOCOL SUMMARY	3
	2.1	Synopsis 3	
	2.2	Schedule of Events	9
3	TAI	BLE OF CONTENTS	14
	3.1	List of In-text Tables	18
	3.2	List of In-text Figures.	18
4	LIS	Γ OF ABBREVIATIONS AND DEFINITION OF TERMS	19
5	INT	RODUCTION	20
	5.1	Background and Rationale	

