9.5 Method of Assigning Subjects to Treatment Groups

In this parallel-group randomized study, subjects who meet study entry criteria will be randomly assigned in a 1:1 ratio to varespladib-methyl or placebo. The randomization schedule will be computer generated using a permuted block algorithm and will randomly allocate IP to randomization numbers. The randomization numbers will be assigned sequentially through a central interactive web response system (IWRS) as subjects are entered into the study. The randomization schedule will be stratified by age group (5 to < 11 years, 11 to < 18 years, and \geq 18 years) and by the presence or absence of neurotoxicity (SSS nervous system subscore of 0–1 or \geq 2) at Baseline, resulting in 6 strata in total. Study center will not be a blocking factor in the randomization schedule. No one involved in the study performance will have access to the randomization schedule before official unblinding of treatment assignment.

The randomization schedule will be prepared by the study contract research organization (CRO) before the start of the study. No subject will be randomized into this study more than once.

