13.1.5 Clinical Pharmacology Analyses

13.1.5.1 Pharmacokinetics

For noncompartmental analysis, plasma concentrations will be listed and summarized at each time point using descriptive statistics; graphical representations will also be provided. The PK parameters will be summarized by dose using descriptive statistics. Testing of PK parameters will be outlined in the SAP.

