## **11.      Other Planned Analysis**

## 11.1. Pharmacokinetic Analysis

Descriptive summaries of the concentration level of varespladib-methyl in plasma and sPLA2 activity at specified timepoints will be tabulated by treatment group.

By-subject concentrations of varespladib-methyl in plasma will also be presented.

The pharmacokinetic characterization of drug concentrations for each dose to be profiled will be performed using noncompartmental analysis (NCA).

The PK parameter estimates will be completed using Phoenix WinNonlin (Pharsight Corporation) software using the actual elapsed times from dose administration to sample collection. For plasma concentration data, all values below the limit of quantification (BLQ) will be set to 0 for summary statistics and graphs. For the PK parameter calculation, BLQ plasma concentrations occurring before Tmax will be set to 0, with the exception of a BLQ value occurring between two measurable concentrations, in which case it will be set to missing.

Standard PK parameters assessed will include measures of the extent of absorption using estimates of the area under the plasma concentration-time curve from time 0 to the time of the last quantifiable plasma concentration (AUC0-t), Area under the plasma concentration-time curve from time 0 to infinity (if data permits) (AUC0-inf) and rate of absorption using the maximum serum plasma concentration (Cmax), the time of Cmax (Tmax), apparent first order terminal elimination half-life (t1/2), apparent terminal phase rate constant ( $\lambda_z$ ) (if data permits). Any subject for whom the portion of the AUC extrapolated to infinity exceeds 20% of the total AUC0-inf will be excluded from the calculation of the descriptive statistics for AUC0-inf.

Other PK parameters may be derived, where appropriate, and as data permit.

For noncompartmental analysis, plasma concentrations will be listed and summarized at each time point using descriptive statistics. Descriptive statistics reported will include the arithmetic mean, SD, CV%, geometric mean, minimum, maximum, and median. Only the range and the median will be reported for Tmax and Tlast, as these are categorical parameters. The PK parameters will also be summarized by treatment using descriptive statistics.

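### Setting BLQ to 0 conflicts with the planned geometric means and semi-log plots, and the 20-subject intensive PK subset should be expected to give only about 10 profiles on active drug

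*Protocol*

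**What the plan says.** **BLQ rule.** SAP 11.1 states that "all values below the limit of quantification (BLQ) will be set to 0 for summary statistics and graphs". For concentrations at each time point, the same section adds: "Descriptive statistics reported will include the arithmetic mean, SD, CV%, geometric mean, minimum, maximum, and median". It also plans individual and mean concentration graphs on both linear and semi-logarithmic scales, with mean graphs by treatment group. Calculation of PK parameters has its own rule: BLQ before Tmax is 0, except that a BLQ between two measurable values is set to missing. Nothing is stated for BLQ after Tmax.

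**Subset.** Protocol 10.3.2.1 says "PK sampling will only be performed for a total of 20 adult and pediatric subjects on Days 1 and 3". The footnote to the Schedule of Events (Protocol 2.2) gives the stopping rule: "Once 20 subjects have provided PK samples for Days 1 and 3, sites will be notified by the sponsor to discontinue" that sampling. For children, Protocol 10.3.2.1 says "Efforts will be made to include at least 4 pediatric subjects from each age tier". Under Protocol 9.5, "subjects who meet study entry criteria will be randomly assigned in a 1:1 ratio to varespladib-methyl or placebo", and Protocol 9.6 keeps sites and study personnel blinded. The PK Population (Protocol 13.1.1, SAP 5) takes any treated subject with at least one evaluable post-dose measurement and is not limited to the active arm.

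**Grouping.** Protocol 13.1.5.1 says "The PK parameters will be summarized by dose using descriptive statistics". SAP 11.1 summarizes the parameters by treatment.

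**The concern.** The BLQ rule and the list of statistics cannot both be followed literally. A geometric mean does not tolerate a zero, and a log axis has no place for one. SAP 11.1 assigns the PK analysis to a third-party laboratory, so the written rule should be executable as it stands. Otherwise the laboratory will choose a convention after seeing the data.

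The second issue is what the number 20 means. Both the stopping rule and the pediatric target count subjects sampled, not subjects on drug. A reader of the protocol could expect 20 drug profiles with at least 4 in each pediatric tier. The plan as written should be expected to give about half of that. AUC, Cmax and Tmax (Protocol 10.3.2.2, SAP 11.1) can come only from the active half, and a by-dose table would have very small pediatric cells.

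**Working it through.** **1. Geometric mean with BLQ = 0.** For n concentrations the geometric mean is exp[(1/n) Σ ln x], or equivalently (Π x)^(1/n). One x = 0 makes the first form undefined (ln 0) and the second equal to 0.

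Where zeros occur:
- Day 1 pre-dose, both arms: no drug has been given, so BLQ is expected throughout.
- Placebo, all times: the same. CV% is also undefined there (0/0).
- Active arm, post-dose: depends on the BLQ rate. The documents give neither a quantification limit nor a rate.

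Assume each sample is BLQ independently with probability q. The chance that a cell of m active subjects contains at least one BLQ is 1 − (1 − q)^m. I use m = 10 for the intensive subset, and m = 55 for the Day 7 pre-dose sample (half of 110, assuming all are sampled):

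| assumed q | m = 10 | m = 55 |
|---|---|---|
| 1% | 0.10 | 0.42 |
| 5% | 0.40 | 0.94 |
| 10% | 0.65 | >0.99 |
| 20% | 0.89 | >0.99 |

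Illustration with 10 simulated log-normal values (assumed median 100, log-scale SD 0.6), setting the lowest to 0:
- geometric mean: 114 to 0
- arithmetic mean: 122 to 117
- median: 124, unchanged
- geometric mean of the 9 remaining values: 127, against 114 for all 10. This is the upward bias from using quantifiable values only.

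**2. Semi-log plots.** An individual zero cannot be drawn. On a mean plot, a cell of zeros only (Day 1 pre-dose, placebo) cannot be drawn. A mixed cell can be drawn if the arithmetic mean is plotted, but not if the geometric mean is. The SAP does not say which mean is graphed.

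**3. Expected active profiles.** The documents give no derivation for 20, so there is no figure to reproduce.
- Whole subset: 20 × 0.5 = 10 active.
- A pediatric tier with exactly 4 sampled: 4 × 0.5 = 2 active.
- Remaining adults: 20 − 8 = 12, and 12 × 0.5 = 6 active.

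A by-dose summary would therefore rest on about 6, 2 and 2 active subjects.

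**4. Spread around those expectations.** Under independent 1:1 assignment the SD is √(20 × 0.25) = 2.24, with a central 95% range of 6 to 14 active. Drawing 20 at random from 55 active and 55 placebo gives the same range. For a tier of 4, P(at most 1 active) = 5/16 = 0.31 and P(none) = 1/16 = 0.06.

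Randomization is by permuted blocks, stratified by age tier and neurotoxicity, so the tier figures depend on block sizes that are not disclosed. Assuming blocks of 4 and the first four subjects in a tier:
- all in one stratum: P(at most 1) = 0, P(none) = 0
- split 3 + 1: P(at most 1) = 0.5 × 0.5 = 0.25, P(none) = 0
- split 2 + 2: P(at most 1) = (1 + 8)/36 = 0.25, P(none) = 1/36 = 0.03

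Across these assumptions P(at most 1) runs from 0 to 0.31. The expected value of 2 does not change.

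**The case against.** The strongest reply is that this is a descriptive PK component with no hypothesis or precision target, and that most of it works. That largely stands. Zeros do not break the arithmetic mean, SD, median, minimum or maximum. Parameter calculation has its own BLQ rule, so Cmax and AUC geometric means in subjects with quantifiable levels are sound. A Day 1 pre-dose geometric mean tells nobody anything under any rule. About 10 active profiles support a descriptive summary by treatment.

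Sampling both arms also protects the blind, so placebo subjects in the subset are not an error. The pediatric target is a best effort at a minimum, so more than 4 per tier may be sampled. However, SAP 6.1.2 anticipates low numbers in both pediatric strata. Day 7 pre-dose sampling covers all subjects, about 55 of them active if all 110 are sampled, but one trough per subject does not give AUC, Cmax or Tmax.

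A reader might infer that the 20 should instead be counted on active assignment. The documents do not favor this:
- To expect 20 active, 20/0.5 = 40 subjects must be sampled. At 14 samples each (8 on Day 1, 6 on Day 3), the extra 20 subjects add 280 samples.
- Even with 40 sampled, the chance of reaching 20 active is only 0.56 under independent assignment.
- Four active per tier needs about 8 sampled per tier, which may not be feasible given the low pediatric numbers anticipated.
- Protocol 9.6 bars unblinded personnel from study procedures.
- Stopping on the nth active subject reveals that the last one sampled is active. A tier stopped after exactly 4 subjects would reveal all four.

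**Conclusion.** Two limited points hold. First, SAP 11.1 contains a rule that fails when followed literally. The geometric mean is 0 or undefined in every cell with a BLQ value. This is expected at Day 1 pre-dose and throughout placebo, and possible in active post-dose cells at a rate the documents do not let one estimate. Second, the intensive subset should be read as about 10 expected active profiles, and about 2 per pediatric tier if exactly 4 are sampled. That rests only on 1:1 allocation and a count that ignores arm.

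A reader might go further and conclude that the PK plan cannot deliver its summaries, or that it fails as the trial's check on the pediatric doses. The documents do not support either. Most planned statistics remain computable, and no section gives the subset that confirmatory role. Protocol 7.2 says only that PK analysis includes pediatric subjects. The tail probabilities should not be quoted as firm, because they depend on undisclosed block sizes. Nothing here touches the primary or key secondary analyses.

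**What to change.** In SAP 11.1:
- Keep BLQ = 0 for arithmetic summaries and linear plots only.
- For geometric means and semi-log plots, use quantifiable values and show the number BLQ in each cell, or report the cell as not calculable. If quantifiable values are used, state that this biases the geometric mean upward when BLQ values are frequent.
- Say which mean the mean graphs show, and how BLQ after Tmax is handled in parameter calculation.
- Limit PK parameter summaries to subjects on active drug.

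In Protocol 10.3.2.1 and the Schedule of Events footnote, or in a SAP note if sampling is already complete: describe the subset as 20 subjects from both arms with about 10 expected active profiles, and about 2 per pediatric tier at the minimum target. Reconcile the by-dose grouping in Protocol 13.1.5.1 with the by-treatment grouping in SAP 11.1. If by-dose pediatric summaries are kept, expect cells of about 2, where individual values say more than an SD.

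The arm-blind stopping rule should stay as it is. The cost is a few sentences before database lock, with no extra samples and no change to the blind. These edits do not add active profiles; they make the stated yield accurate.
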